3. PURPOSE AND OBJECTIVES OF RESEARCH

Objective: To evaluate the efficacy, safety and tolerability of Bioven in patients with chronic primary immune thrombocytopenia, with evidence of non-inferiority compared to the literature data regarding the level of effectiveness of existing IVIG products.

Tasks of study:

- To evaluate the proportion (%) of patients who achieved the response (R) during the study, platelet count> 30x10⁹ / 1 and at least double their initial number, as confirmed by at least 2 blood tests performed every 7 days; absence of bleeding) during therapy with the studied drug Bioven.
- To evaluate the effeciency of the studied drug Bioven in comparison with the literature data
- To evaluate the presence and severity of hemorrhagic syndrome as a result, which is included within 4 weeks after starting therapy;
- To evaluate the proportion (%) of patients who achieved a complete response (CR) during the study (platelet count> 100 x 10^9 / l, confirmed by at least 2 blood tests performed every 7 days; no bleeding) during treatment with the study drug Bioven.
- To evaluate the proportion (%) of patients who did not respond (NR) during the study with a platelet count $<30 \times 10^9$ / L or less than a 2-fold increase in platelet count from baseline. This must be confirmed by at least 2 blood tests with a difference of one day, or the presence of bleeding during therapy with the study drug Bioven.
- To evaluate the proportion (%) of patients who lost the response (R) during the study (a decrease in platelet count (<30 x 10^9 / L, or less than twice the initial or bleeding. Platelet counts should be confirmed at least twice with an interval of 1 day).
- To evaluate the proportion (%) of patients who lost a complete response (CR) during the study, a decrease in platelet count, $<100 \times 10^9$ / l, or the occurrence of bleeding. Platelet counts should be confirmed at least twice with an interval of 1 day).
- To determine the time from the start of treatment with the study drug Bioven to the onset of the response (R);
- To determine the time from the start of treatment with the studied drug Bioven to the onset of a complete response (CR);
- To set the duration of the response (R);
- To set the duration of the complete response (CR);
- To evaluate the frequency and severity of possible adverse events/adverse reactions (AE/AR).
- To evaluate the frequency of clinically significant changes in laboratory parameters after infusion of the study drug using the study drug Bioven.
- To evaluate the frequency of clinically significant changes in vital signs after infusion of the study drug using the study drug Bioven.

4. STUDY DESIGN

4.1. Model description, number of patients, groups

Study design: open-label, multicenter, international, non-randomized, non-controlled, singlegroup study evaluating the efficacy, safety and tolerability of Bioven, 10% solution for infusion.

Number of patients: The number of subjects in Ukraine and worldwide is 40 patients: men and women aged 18-65 years with a confirmed diagnosis of chronic primary immune thrombocytopenia (at least 12 months from the date of diagnosis). In Ukraine, no more than 36 patients will be enrolled.

Groups: This study does not provide for the division of patients into groups. Patients who have been screened and meet the inclusion criteria, who do not have non-inclusion (exclusion) criteria and those who have signed the Informed Consent Form (ICF), are included in the study, and receive the study drug (SD).

4.2 Stages of the study. Screening

The patient or his or her legal representative must sign an informed consent form.

After signing the informed consent form, the screening surveys are performed and the compliance with the inclusion / non-inclusion criteria is assessed.

At the screening stage, verification of the diagnosis of chronic primary ITP is required (based on primary documentation data) (Section 6.5.3 of the Protocol).

4.3 Stages of the study. Clinical stage

The stage starts after the screening is completed.

Patients receive the study drug Bioven, solution for infusion of 10%, at a dose of 0.8-1.0 g / kg 1 time per day for 2 consecutive days (course dose 1.6 - 2.0 g / kg).

The time of administration of the studied drug, the occurrence of adverse events is recorded in the CRF.

Prescribed therapy and examination results are recorded in the CRF based on primary documentation.

The CRF data are entered according to the patient's management plan (Section 6 of the Protocol). Patients participating in this study may receive corticosteroid therapy if the patient is taking long-term and stable doses (at least 2 weeks before screening). Increasing the dose of corticosteroids less than 2 weeks before, during, and after SD administration is considered an ineffectiveness of SD.

If the patient has been treated with cyclophosphamide, azathioprine or attenuated androgens, the treatment regimen and dose should be stable for at least 2 months before day 0 (immunosuppressant dose should remain unchanged until day 30).

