Bioven should be administered intravenously dropwise at the initial rate of 0.5-1.0 ml/kg of body weight/hour for 30 minutes. If no adverse reactions occur, the rate of administration may be gradually increased (it is recommended to increase by 0.5-1.5 ml/kg of body weight/hour every 10 min). According to the data from clinical studies the maximum rate of administration is 8.5 ml/kg of body weight/hour.

The study drug is administered only in hospital environment while observing the rules of aseptic. The solution should be of room temperature before use. Cloudy solutions and those containing sediment are not used. For the administration of the drug, it is necessary to use a separate infusion system.

When administering the drug, it is necessary to consider the information specified in the relevant sections of the instructions for medical use: administration details, special safety measures, contraindications, interaction with other medicinal products, etc.

Patients participating in this study may receive concomitant therapy, which is used for the treatment of comorbidities and life-threatening conditions.

It is allowed to use glucocorticoids in a stable dose for at least 2 weeks before starting treatment with the test drug. The need to increase the dose of corticosteroids during the study is considered as ineffective use of the study drug.

Duration of treatment:

The duration of treatment with the study drug for each patient is no less 2 days. The total period of stay in the study is 4 weeks.

Efficacy and safety endpoints: Efficacy:

Primary efficacy endpoint:

| Bioven | |
|----------------------------|--|
| Trial Code: 2021-BV-ITP-BP | |

Page 11 Version 1.4 from July 03, 2023,

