- Patient's wish
- Occurrence of severe and/or unexpected AE/AR in patient during the study, that require discontinuation of the drug;
- The need to prescribe drugs prohibited in this study.
- Significant deterioration of the patient's condition during the study period;
- Failure of the patient to adhere to the treatment regimen;
- Failure of the patient to follow the procedures established under the protocol;

Due to the variability of PLT levels in patients with chronic immune thrombocytopenia (wave), it is possible to re-screen or extend the duration of the screening phase, but only if the subject meets all other specified inclusion criteria and has no inclusion or exclusion criteria.

Patients who drop out at the screening stage are not included in the efficacy and safety analysis, as they do not receive any doses of the investigational drug (ID).

Patients who do not receive a full course of study drug are included in the safety analysis but not in the efficacy analysis.

Patients who dropped out of the study after completion of SD administration during the followup period are considered in the efficacy and safety analysis. The data of such patients are evaluated by parameters that can be analyzed at a certain point in time. The dropped data are not analyzed.

For all patients who complete the study due to AE, requiring discontinuation of treatment with the studied drugs, it is necessary to conduct the procedures of the final visit in the near future after the development of AE. After stopping treatment, the patient should be monitored until the reaction disappears or its clinically significant signs. Patients who received at least 1 dose of SD but prematurely dropped out of the study are included by the investigator in the analysis of tolerability of the study drug.

The reasons for premature withdrawal from the study are indicated in the Individual registration form.

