8 EVALUATION OF EFFICIENCY

8.1 Primary efficacy endpoint:

Part (percent) of patients with response (R).

R is determined according to the following criteria:

- Patients with R: platelets count $> 30x10^{9}/L$ and at least a two-fold increase from the baseline count. This must be confirmed by at least 2 blood tests at least 7 days apart, and the absence of bleeding;

The primary efficacy variable is achievement of R during the study (yes/no).

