10.3.3. Analysis of effectiveness

Additional information about the statistical model for evaluating the effectiveness of the drug by the main variable is given in Section 10.1. "The content of statistical analysis".

A) The primary outcome of efficiency – Proportion (%) of patients with response (R).

Primary efficiency variable – achievement of R during the study. *R is defined according to criteria* *:

| Bioven | Page 71 |
|----------------------------|--------------------------------|
| Trial Code: 2021-BV-ITP-BP | Version 1.4 from July 03, 2023 |

- Patients with R: the number of platelets > $30x10^{9}/l$ and at least a two-fold increase from the baseline count. This must be confirmed by at least 2 blood tests performed once every 7 days and the absence of bleeding;

The categories of the variable will be defined as "Yes" or "No" respectively.

* The criteria are defined according to the Guideline on the clinical investigation of human normal immunoglobulin for intravenous administration (IVIg), EMA/CHMP/BPWP/94033/2007 rev. 4, 16 December 2021 as well as according to the criteria of the international working group on ITP in 2009. (Rodeghiero, F., Stasi, R., Gernsheimer, T., Michel, M., Provan, D., Arnold, D. M., ... & George, J. N. (2009). Standardization of terminology, definitions, and outcome criteria in immune thrombocytopenic purpura of adults and children: report from an international working group. Blood, The Journal of the American Society of Hematology, 113(11), 2386-2393.);

B) Secondary effectiveness variables.

For variables assessed once at the final visit, descriptive statistics methods will be used to describe these variables (for quantitative parameters - n, arithmetic mean, median, standard deviation, minimum and maximum value; for categorical parameters - number and share in %). 95% confidence intervals will be calculated. In the case of measuring variables at more than two visits, one-way analysis of variance (ANOVA) methods will be used.

Censored data will be analyzed using the Kaplan-Meier method or the log-rank test.

Secondary efficacy endpoints are transformed into corresponding efficacy variables:

Achieving a complete response (CR) during the study.

CR is determined according to the criteria *:

 Patients with CR: platelets count > 100 x 10⁹/L, which is confirmed by 2 blood tests performed at least 7 days apart and the absence of bleeding;

The categories of the variable will be defined as "Yes" or "No" respectively.

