10.4. Data set for analysis

ITT (Intention-to-treat population) - all study participants who took the study drug at least once. Data from this sample will be used for safety analysis.

PP (Per Protocol) - all patients who met the requirements of the protocol. This population includes all patients who received protocol therapy in full, completed all scheduled visits, and had no significant protocol deviations. The data obtained on this sample will be used for analysis according to the criteria of drug effectiveness.

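### The definition of response has no rule for added ITP treatment, so such patients may count as responders or leave the efficacy set; near the margin, both favour non-inferiority

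*Combined protocol and SAP*

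**What the plan says.** **Corticosteroids.** Section 4.3: "Increasing the dose of corticosteroids less than 2 weeks before, during, and after SD administration is considered an ineffectiveness of SD". The synopsis: "The need to increase the dose of corticosteroids during the study is considered as ineffective use of the study drug".

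**Definition of R.** Section 8.1 requires platelets above 30 x 10⁹/L and at least a doubling from baseline, and adds: "This must be confirmed by at least 2 blood tests at least 7 days apart, and the absence of bleeding". Section 10.3.3 repeats the thresholds with: "This must be confirmed by at least 2 blood tests performed once every 7 days and the absence of bleeding". The primary variable is whether R is achieved during the study, yes or no. Neither section mentions corticosteroids or any other treatment.

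**Other treatment.** The synopsis states: "Patients participating in this study may receive concomitant therapy, which is used for the treatment of comorbidities and life-threatening conditions". Section 7.6 bars monoclonal antibodies and avatrombopag and requires stable immunosuppressant doses, as does 4.3. Section 5.2 lists other immunoglobulins and cytostatics as incompatible. On-study platelet transfusion and other thrombopoietin-receptor agonists are not named.

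**Who is analysed.** Under 5.3 a patient may be excluded for "The need to prescribe drugs prohibited in this study". Section 5.3 also says: "Patients who dropped out of the study after completion of SD administration during the followup period are considered in the efficacy and safety analysis". Section 10.4 bases efficacy on the per-protocol set, meaning patients who had full therapy, "completed all scheduled visits, and had no significant protocol deviations". Section 11.2 lists departures from protocol therapy among significant deviations without naming rescue treatment.

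**Repeat course.** The synopsis, 6.2 and 7.4 allow a second Bioven course 14 to 28 days after the first infusion. The synopsis adds only that the length of follow-up ignores it.

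**The concern.** The trial has one arm and no control. A platelet rise can be credited to Bioven only if nothing else that raises platelets was added. The sponsor accepts this for corticosteroids, but a statistician who derives R from 8.1 or 10.3.3 as written would not apply even that rule.

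A patient who fails Bioven and then gets other treatment can go one of two ways. If the counts rise and there is no bleeding, the definition scores R. If the patient is withdrawn or classed as a significant deviation, a likely failure leaves the denominator. The second route is itself unclear, because 5.3 keeps patients who leave after full dosing in the efficacy analysis while 10.4 requires every scheduled visit. Either way the observed rate goes up, and the choice would be made in an open-label study with the counts known.

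**Working it through.** **Inputs.** Section 10.2: reference rate 0.78 in 82 patients, margin -0.25, two-sided 5%. Section 10.1: Wald interval for the difference, using both variances. Patient numbers: 29 (calculated minimum), 36 (after dropout, 10.2) and 40 (synopsis and 4.1).

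**The plan's own figure.** (1.96 + 1.28)² x 0.78 x 0.22 / 0.25² = 28.8, so 29. Then 29/0.8 = 36.25; the plan uses 36. Both reproduce to rounding.

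**Timing.** Scheduled counts fall at 48 hours and Days 7, 14, 21 and 28. R needs two qualifying counts at least 7 days apart. Added treatment can supply both scheduled counts only if it starts before the Day 21 count. After that it can supply at most the confirming count.

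**Cut-offs.** Lower limit = p - 0.78 - 1.96 x sqrt(p(1-p)/n + 0.78 x 0.22/82); non-inferiority if above -0.25.

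- 25/36: -0.261, fails.
- 26/36 (one patient rescored as R): -0.229, passes.
- 25/35 (one failure removed): -0.240, passes.
- 28/36 (close to the planned 78%): -0.165, passes. Taking one responder away leaves 27/36, still above the cut-off of 26.

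The smallest passing counts are 21/29, 26/36 and 28/40. After removing one failure they are 21/28, 25/35 and 28/39; after removing two, 20/27, 25/34 and 27/38.

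**Chance of a false conclusion at the margin.** The true rate there is 0.78 - 0.25 = 0.53. Let X be binomial(n, 0.53), with the reference rate taken as fixed, and let c be the smallest passing count. If k would-be non-responders are counted as R, the chance is P(X ≥ c for n, less k). If k are dropped, it is P(X ≥ c for n - k).

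| n | none | 1 counted as R | 2 counted as R | 1 dropped | 2 dropped |
|---|---|---|---|---|---|
| 29 | 0.0265 | 0.061 | 0.122 | 0.0265 | 0.061 |
| 36 | 0.015 | 0.034 | 0.069 | 0.034 | 0.034 |
| 40 | 0.022 | 0.045 | 0.086 | 0.022 | 0.045 |

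The two-sided 5% level implies 0.025 on this side.

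**How often one patient decides at n = 36.** The chance of exactly 25 responders is 0.02, 0.07, 0.14 and 0.07 at true rates of 53%, 60%, 70% and 78%.

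**Range by assumed frequency.** The documents give none. Suppose 5%, 10% or 15% of all patients meet R only through added or repeat treatment and are scored R, on top of a 53% rate without it. Then at n = 36 the chance of declaring non-inferiority is P(X ≥ 26) at 58%, 63% and 68%: 6%, 17% and 37%. These shares are assumptions.

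**Dependence on the test.** Section 10.1 also offers a one-sample criterion without the reference variance. With it the cut-off at n = 36 is 25, so the sensitive result moves to 24/36.

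**The case against.** Three points on the other side carry weight.

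*The corticosteroid rule exists.* A reader might infer that the plan leaves a corticosteroid increase unscored. The documents do not support that. Calling it ineffectiveness, when 10.3.7 describes the positive outcome of the primary variable as the drug being effective, most naturally means R = No. What is missing is the link to the endpoint definition.

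*Most alternatives are barred or restricted.* A reader might also infer that any rescue treatment can be counted as a Bioven response. For other immunoglobulins, cytostatics, monoclonal antibodies, avatrombopag and immunosuppressant changes, withdrawal or a significant deviation is the likelier result. That leaves platelet transfusion and other thrombopoietin-receptor agonists as the plainer gap. But removal is not neutral: it takes a likely failure out of the denominator. Relying on a per-protocol set is a wider matter, but the scoring of these patients can be settled on its own.

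*The repeat course is study treatment.* It is tempting to call R after a second course an error. Since the course is permitted and R may be reached at any time during the study, counting it is a fair reading. Restricting R to one course answers a different question, and the choice is the sponsor's. The synopsis remark on follow-up length is not a scoring rule either way.

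In addition, a patient treated because of bleeding will tend to fail R on the bleeding criterion.

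**Conclusion.** The gap is real and should be closed, but its reach is limited. The definition of R does not carry the corticosteroid rule, does not address treatments left unnamed, and does not keep patients given barred treatment in the denominator. At n = 36 and a true rate of 53%, one would-be non-responder handled either way moves the false-conclusion chance from 0.015 to 0.034, across the implied 0.025. At n = 29 or 40, dropping one patient moves nothing, while counting one as R does.

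A reader might infer that the primary conclusion is generally unsafe. The documents do not support that: close to the planned rate one patient has no effect, and no frequency of added treatment is given. The figures assume the two-variance Wald interval, a fixed reference rate, and affected patients who would otherwise be non-responders, do not bleed and, where counted as R, reach two qualifying counts.

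**What to change.** Add to 8.1 and 10.3.3:

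1. Platelet counts after a corticosteroid increase, a platelet transfusion, or the start or increase of any non-study ITP treatment do not count towards R or CR.
2. The patient stays in the efficacy denominator as R = No unless R was already confirmed.
3. Such treatment is not a reason for removal from the efficacy set. This settles 5.3 against 10.4 for these patients.

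For the repeat Bioven course, keep the sponsor's choice of primary rule. Report how many patients were re-treated, and give R based only on counts before the repeat course as a sensitivity analysis.

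The cost is protocol wording, one derivation rule and one extra analysis. Prescribed therapy and study drug administration times already go into the CRF (4.3, 6.2). The downside is a response rate that may be slightly lower.

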The route of administration and dosage doesn't exceed the maximum single and course doses that can be used in the treatment of patients, according to the approved Instructions for medical use of the drug Bioven. They fully meet the requirements for the finished medicinal product, which are strictly regulated by the European Pharmacopoeia (monograph Eur. Ph.0918), the State Pharmacopoeia of Ukraine, and are within the limits set out in the Guideline on core SmPC for human normal immunoglobulin for intravenous administration (IVIg) EMA / CHMP / BPWP / 94038/2007 Rev. 5 June 28, 2018.

7.5 Concomitant therapy is allowed.

The use of any drugs other than those listed in section 7.4 is permitted. Patients should refrain from unprotected sexual intercourse throughout the study. Within 30 days of completion, study participants with preserved reproductive potential should use effective barrier contraception. The purpose of barrier contraception is to prevent sexually transmitted diseases, including HIV, HBV, HCV.

Effective methods of contraception include:

• Full maintenance;

• Condom or double barrier method.

7.6 Concomitant therapy is prohibited.

The following drugs are prohibited during the participation of patients in a clinical trial:

- 1. Corticosteroids are allowed only if the patient is taking long-term stable doses at least 2 weeks before screening;
- The dose of corticosteroids or other immunosuppressant should remain unchanged for up to 31 days;
- 3. If patients have been treated with cyclophosphamide, azathioprine or attenuated androgens, the treatment regimen should be stable for at least 2 months before Day 0;
- 4. Monoclonal antibodies;
- 5. Avatrombopag;
- 6. Antiplatelet agents;
- 7. Anticoagulants.

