8.2 Secondary efficiency endpoints

Part (percent) of patients with a complete response (CR).

CR is determined according to the following criteria:

- Patients with CR: platelets count > 100 x 10^{9} /L, which is confirmed by 2 blood tests performed at least 7 days apart and the absence of bleeding;

Part (percent) of patients with no response (NR).

NR is determined according to the following criteria:

- Patients with NR: platelet count $< 30 \times 10^{9}$ /L or less than two-fold increase of baseline platelet count. This must be confirmed by at least 2 blood tests performed approximately 1 day apart, or the presence of bleeding;

Part (percent) of patients with loss of response (loss of R).

Loss R is determined according to the following criteria:

- Patients with loss R: a decrease platelet count < 30×10^9 /L or less than two-fold increase of baseline platelet count, or the occurrence of bleeding. Platelet counts confirmed at least 2 blood tests performed approximately 1 day apart.

Part (percent) of patients with loss of complete response (loss of CR).

CR loss is determined according to the following criteria:

- Patients with loss of CR: decrease platelet count < 100 x $10^9/L$, or the occurrence of bleeding. Platelet counts confirmed at least 2 blood tests performed approximately 1 day apart.

Time (in days) from treatment start to onset of a response (R); Time (in days) from treatment start to onset of a complete response (CR); Duration (in days) of response (R); Duration (in days) of complete response (CR);

Secondary efficacy endpoints are transformed into corresponding efficacy variables

Safety

- Frequency (percent) of adverse events

- Frequency (percent) of serious adverse events

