10.3.7. Conclusion on non-inferiority effectiveness

In accordance with EMA recommendations for clinical studies of immunoglobulin normal for intravenous administration (*Guideline on the clinical investigation of human normal immunoglobulin for intravenous administration (IVIg)*, *EMA/CHMP/BPWP/94033/2007 rev. 4, 16 December 2021)* the obtained results will be compared with literature data The conclusion of non-inferiority of the drug Bioven, solution for infusions 10%, in the treatment of chronic immune thrombocytopenia, will be made according to the main efficacy variable using an approach based on confidence intervals. To do this, the calculated limits of the 95% confidence interval (CI) for the difference in the

percentage of positive results according to the main variable ("the drug is effective") for the studied group must be compared with the limit of the non-inferiority zone - effectiveness that is not inferior (-25%) to the calculated based on data for comparison. If the lower limit of the CI is greater than the

| Bioven | Page 74 |
|----------------------------|--------------------------------|
| Trial Code: 2021-BV-ITP-BP | Version 1.4 from July 03, 2023 |

lower limit of the non-inferiority zone (non-inferiority), then it will be considered that the study drug is not inferior in effectiveness compared to literature data.

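### A corticosteroid dose increase counts as ineffectiveness of Bioven in the synopsis and 4.3, but the primary variable R, CR and section 10 do not carry that rule

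*Combined protocol and SAP*

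**What the plan says.** Two places give an outcome rule for corticosteroids. Section 4.3: "Increasing the dose of corticosteroids less than 2 weeks before, during, and after SD administration is considered an ineffectiveness of SD". The synopsis, under the dose schedule: "The need to increase the dose of corticosteroids during the study is considered as ineffective use of the study drug".

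The variable that is tested does not contain this rule. Under 8.1 and 10.3.3 A, R needs a platelet count above 30 x 10⁹/L that is at least double the baseline. Section 10.3.3 A then adds: "This must be confirmed by at least 2 blood tests performed once every 7 days and the absence of bleeding". CR, NR, loss of R and loss of CR (8.2 and 10.3.3 B) are likewise built from platelets and bleeding alone. Sections 10.1 to 10.5, including missing data, analysis sets and the non-inferiority conclusion, do not mention corticosteroids. Section 10.3.7 bases the conclusion on the "percentage of positive results according to the main variable ('the drug is effective') for the studied group".

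Three other sections bear on such a patient:
- Section 7.6, on prohibited therapy: "The dose of corticosteroids or other immunosuppressant should remain unchanged for up to 31 days".
- Section 5.3 allows the investigator to withdraw a patient for "The need to prescribe drugs prohibited in this study", but keeps patients who leave after full dosing in the efficacy analysis.
- Section 10.4 runs efficacy on the per-protocol set, which excludes significant deviations; 11.2 gives examples of these.

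**The concern.** The trial has a single arm and allows background corticosteroids, which section 2.1 lists among first-line treatments for ITP. If the dose is raised after Bioven and the platelets then rise, the rise cannot be credited to Bioven. The plan recognised this and stated how to treat it, but did not carry the rule into the definition that the analyst will program. Two parts of the same document therefore give opposite answers for the same patient. The answer that comes from following section 10 literally is the one that helps the drug.

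**Working it through.** **Side by side.** Take a patient on a stable corticosteroid dose who receives both infusions and has the dose raised on Day 3. Counts on Days 7 and 14 are above 30 x 10⁹/L and at least double the baseline, with no bleeding.

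- 8.1 and 10.3.3 A: every listed criterion is met, so R = Yes.
- Synopsis and 4.3: the increase means Bioven was ineffective, which for a variable labelled as the drug being effective can only be No.
- 7.6, 11.2 and 10.4 together: the increase breaks the unchanged-dose requirement, could be judged a significant deviation, and would then remove the patient from the per-protocol set. This needs a judgement that no section makes, and 5.3 points towards keeping the patient.

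**Inputs for the arithmetic.** Reference rate p0 = 0.78 with n0 = 82, and margin -0.25 (10.1, 10.2); two-sided 95% Wald interval for the difference (10.1); pass if the lower limit exceeds -0.25 (10.3.7). Evaluable size: (1.96 + 1.28)² × 0.78 × 0.22 / 0.25² = 10.4976 × 0.1716 / 0.0625 = 28.82, which reproduces the plan's 29. The plan also gives 36 after dropout and 40 as the total number of patients.

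Lower limit = x/n - 0.78 - 1.96 × √[(x/n)(1 - x/n)/n + 0.78 × 0.22/82]

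For 26/36: 0.7222 - 0.78 - 1.96 × √(0.005573 + 0.002093) = -0.0578 - 0.1716 = -0.229.

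**One raised-dose patient exactly at the threshold**

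| n | scored Yes | scored No | excluded |
|---|---|---|---|
| 29 | 21/29: -0.242, pass | 20/29: -0.281, fail | 20/28: -0.256, fail |
| 36 | 26/36: -0.229, pass | 25/36: -0.261, fail | 25/35: -0.240, pass |
| 40 | 28/40: -0.248, pass | 27/40: -0.276, fail | 27/39: -0.258, fail |

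The reversal between Yes and No holds by construction: taking one responder from the smallest passing count always fails. What the table adds is where the threshold lies, and that exclusion raises the lower limit relative to No at each size but reverses the verdict only at 36.

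**Slack away from the threshold, at about 78% response**

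- n = 29: 23 responders; rescoring two leaves 21 (pass), three leaves 20 (fail).
- n = 36: 28 responders; rescoring two leaves 26 (pass), three leaves 25 (fail).
- n = 40: 31 responders; rescoring three leaves 28 (pass), four leaves 27 (fail).

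**The case against.** The best defence is that protocol and SAP are one document, the rule is stated twice without qualification, and the main variable is labelled as the drug being effective. Read as a whole, a raised-dose patient is a failure, and all that is missing is a cross-reference. It stands that No is the only scoring consistent with the stated rule. But 10.3.3 A gives a self-contained definition with Yes/No categories and refers the reader only to 10.1, which has no corticosteroid rule. Someone programming from section 10 would score Yes.

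A second defence is that increases are prohibited and so should be uncommon. The rate is indeed unknown. Still, the plan foresaw increases well enough to give them an outcome.

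A reader might also infer that the plan leaves three equally open scorings, exclusion among them. The documents do not support that. No section labels a corticosteroid increase a significant deviation. The item on inconsistent therapy in 11.2 concerns the schedule of treatment and is paired with study-drug packaging, so it may mean Bioven administration only. Withdrawal under 5.3 is discretionary, and 5.3 keeps fully dosed drop-outs in the efficacy analysis. What keeps exclusion possible is mainly the general wording in 11.2 on deviations that could distort the main results, together with the per-protocol definition in 10.4.

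**Conclusion.** The conflict is real: the synopsis and 4.3 make a corticosteroid increase a failure, and the definition of R used in the test does not. Exclusion from the per-protocol set is a secondary possibility. Both departures from No favour the drug, since Yes adds a responder and exclusion takes a failure out of the denominator.

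The size is limited. It depends on how many patients have the dose raised and then meet the platelet criteria, which the documents do not give and which may be none. The scoring decides the conclusion only near the threshold; at about 78% response the conclusion survives two rescored patients at n = 29 or 36, and three at n = 40. A reader might infer that the risk of a false non-inferiority claim is materially raised. Any such figure would rest on an assumed rate of increases, so none is claimed. The point should be fixed because the repair is cheap and the error, if it occurs, runs in one direction.

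**What to change.** - **Synopsis, 8.1 and 10.3.3 A:** state that starting a corticosteroid, or raising its dose, from Day 0 and before R is confirmed means R = No. Add the matching sentence for CR in 8.2 and 10.3.3 B. Starting must be named, because a patient not previously on corticosteroids raises the same difficulty.
- **8.2 and 10.3.3 B:** state that an increase after confirmed R counts as loss of R from that date, so that a response already confirmed is not overturned. The synopsis and 4.3 make no such exception now, so amend both to match.
- **5.3 and 10.4:** state that such a patient stays in the efficacy denominator.
- **4.3:** delete the clause on increases in the two weeks before dosing, which calls a drug ineffective before it is given. Treat an increase between screening and Day 0 as an eligibility failure, since the only scheduled platelet count before dosing is at screening.

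The cost is a few sentences, with no new visits or tests. Section 4.3 already has prescribed therapy recorded in the CRF; check that this captures the date and size of any corticosteroid change. The downside is that the observed R rate may be slightly lower.
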